## RESEARCH/PROJECT REVIEW APPLICATION

HMRI  
 HealthEast  
 Non HealthEast

*This form fulfills both Research and IRB requirements for HealthEast. Please complete all questions, even if you are not applying for IRB approval.*

### 3 Abstract (500 words or less, do not refer to "see protocol" for abstract):

This abstract should consist of two paragraphs, written in lay language, labeled Background and Methods. They should briefly describe the problem being addressed in the study, including the hypothesis or study question and how the study will be performed.

***Background.*** Achieving spinal fusion requires bone graft and is most reliable using an anterior/posterior technique. The bone graft is placed between the vertebral bodies during the anterior fusion and placed in and adjacent to the facet joints for the posterior fusion. Because there is greater bony surface area between the vertebral

bodies, this area has a more reliable fusion success rate. Instrumentation which helps stabilize the vertebra during the healing period also increases the fusion rate. The bone graft for the posterior fusion may come from a variety of sources. Historically, bone graft was obtained from the iliac portion of the patient own pelvis, IBG, but this resulted in additional postoperative pain (sometimes worse than the fusion wound). Alternatives are currently the most common form of bone graft, but there is very little knowledge as to the superiority of one alternative over another. The purpose of this research is to determine the ability to achieve a solid posterior spinal fusion using sources to bone graft coming from the patient's own iliac crest, or from bone morphogenic protein (BMP), which is costly, but known to give very high fusion rates when applied anteriorly, or from donor bone combined with stem cells derived from either donor bone, fat, or amniotic membrane/fluid (placenta or "afterbirth" tissue).

**Methods.** Patients who are surgical candidates for a one-level anterior/posterior lumbar fusion will be randomized to IBG or one of 4 types of bone graft alternatives (small Medtronic Infuse BMP, Orthofix Trinity allograft bone marrow derived stem cells combined with morcelized cancellous allograft, Allosource Allostem fat derived stem cells combined with morcelized cancellous allograft, or Nutech Nucel amnion derived stem cells combined with morcelized cancellous allograft). There will be 20 patients in each group. All anterior fusions will use BMP; the study only applies to the posterior fusion. Neither patient nor surgeon is blinded to the posterior type of bone graft. The volume of bone graft is the same for each type, approximately 5cc. The decortication part of the fusion is identical for all patients, as is the type of instrumentation (anterior plate and posterior facet screws). Limited CT scans of the fusion will be obtained at approximately one year postoperatively to assess fusion success of both anterior and posterior regions. The limited CT scan results in approximately 2.88 mSv radiation exposure, or similar to one year's worth of background radiation. Secondary endpoints are patient outcomes for pain and function using standard VAS pain scales and Oswestry Disability Index at one year postoperatively will be assessed to ascertain the relationship between clinical success and fusion success since prior studies suggest that success is only related to the status of anterior fusion.

**4 Study Design/Protocol** (Please answer the questions below and attach the study protocol):

- a. What are the objectives of the proposed research/project?

*Evaluate the effectiveness of 5 types of bone graft material in obtaining a solid posterior fusion for one level anterior/posterior lumbar spinal fusion.*

- b. What is the significance of the proposed study? (Provide the context for the study, and the rationale. What is known about the topic? Why is the study important? What kind of answers will the study provide?)

*Iliac bone autograft is an additional procedure with known morbidity and high rate of residual pain postoperatively at the graft donor site leading to reduced outcomes. Bone morphogenic protein is effective in obtaining fusion but is used off label, has multiple side effects, and is expensive to hospital systems. Stem cell bone products are an attractive alternative that avoids pain related to the graft donor site and have a far better safety profile than BMP.*

- What will subjects be asked to do?

*Patients who are scheduled to undergo a single level lumbar anterior/posterior spinal fusion with instrumentation will be eligible to participate. Subjects will be asked to agree to be randomized to one of five types of bone graft for the posterior portion of their fusion surgery.*

- What is the study design?

*Prospective, non-blinded, randomized study design of 5 types of bone graft material applied to 100 patients (20 patients per group).*

- c. Describe the proposed data collection procedures. Attach any forms such as surveys, chart abstraction or other data collection forms.

*Data collection includes age, date of surgery, date of follow-up CT scan (>9 months postop), assessment of fusion at follow-up, smoking and osteoporosis status (which may affect fusion status), type of bone graft used for the anterior procedure (all will be bone morphogenic protein combined with local autograft), type of bone graft used for the posterior procedure.*

- d. List the routine medical related costs for this research/project/trial.

- 1) **ROUTINE OR STANDARD MEDICAL CARE:** This includes items or services that are typically provided absent a clinical trial and those required for the provision of the investigational item or service, as well as appropriate monitoring, prevention of complications, and the diagnosis or treatment of complications arising from the provision of an investigational item or service.

*The fusion surgery is considered standard of care. The costs of a single level lumbar fusion is information known to HealthEast as they are the entity that charges for this type of surgery. The charges and reimbursement for spinal surgery at HealthEast has not been shared with the investigator.*

- 2) **STUDY RELATED CARE:** List the additional items or services required for the provision of the investigational item or service

*Additional items related to cost are limited CT scan at >9months postoperatively. This cost is \$265 per patient and will be paid for by the principal investigator/Midwest Spine & Brain Institute.*

3) **STUDY SPECIFIC CARE:** List items or services furnished solely to satisfy data collection, analysis needs, or to determine trial eligibility.

*Data will be collected by the PI on a personal password protected laptop computer. Statistical analysis will be obtained from a third party.*

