## 6 Subject Population

- a. Check all that apply:  
 Inpatient     Outpatient     Healthy Volunteers     Other
- b. Describe criteria for inclusion and exclusion of subjects in this study:
  - Inclusion Criteria:  
*Lumbar spinal fusion of a single segment for a degenerative condition; age 18 – 65*
  - Exclusion Criteria:  
*Prior lumbar fusion surgery; prior abdominal surgery precluding access to the anterior spine; lytic spondylolisthesis; high grade stenosis requiring partial or complete facetectomy*
- c. If the study includes use of clinical patients, will approval be obtained from the attending M.D.?  
 NO       YES - Describe how:

*Consent will be obtained at the time of preoperative discussion in patients who desire to proceed with fusion surgery after having failed non-operative treatment for their degenerative condition. Risk and benefits of surgery as well as specific risks related to bone graft products will be presented.*

d. How many subjects do you plan to enroll?

100

e. Please indicate the approximate number of subjects to be enrolled for each gender category:

40 Male      60 Female

f. Expected Age Range-please check all that apply:

0-7 (include parental consent form)  
 8-17 (include parental consent form and child assent form)  
 18-65  
 65 and older

Exact ages to be included:18-65

g. Protected Populations to be Studied-please check all that apply

Pregnant women  
 Embryos/Fetuses  
 Prisoners  
 Minors (under age 18)  
 Mentally/Emotionally/Developmentally Disabled Persons  
 NA

h. If this is a multi-center study, what is the total number of subjects to be enrolled from all centers:

NA

i. How will subjects be chosen? (e.g. records, classes, referral)

*Patients who are followed and treated for their spinal condition and who meet the entry criteria will be enrolled from the PI's clinical practice.*

j. Will subjects receive any inducements or rewards for participating in the study?

NO       YES - Please explain:

k. Will subjects be charged for any research-related procedures?

NO       YES - If amount is known, please list:

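### Patients may know their CT fusion result, and their graft, before they score the one-year VAS and Oswestry that are to be related to fusion

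*Protocol*

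**What the plan says.** **Blinding.** Section 3 (Abstract, Methods) says: "Neither patient nor surgeon is blinded to the posterior type of bone graft". Section 4b, under study design, likewise calls the trial non-blinded. Neither place gives a reason.

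**Patient-rated outcomes.** Section 3 continues: "Secondary endpoints are patient outcomes for pain and function using standard VAS pain scales and Oswestry Disability Index at one year postoperatively". Their purpose is "to ascertain the relationship between clinical success and fusion success since prior studies suggest that success is only related to the status of anterior fusion". No comparison of VAS or Oswestry between arms is stated.

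**Timing of the CT.** Section 3 puts the scan at about one year. Sections 4c and 4d(2) require only that it be more than nine months after surgery.

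**What patients are told or can find out.** At consent (section 6c), "Risk and benefits of surgery as well as specific risks related to bone graft products will be presented". Section 8a adds that patients can access their medical record, including the operative report, which shows the graft used.

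**What the patient might notice.** Section 4b says: "Iliac bone autograft is an additional procedure with known morbidity and high rate of residual pain postoperatively at the graft donor site". Of the three cell-based products it says: "Stem cell bone products are an attractive alternative that avoids pain related to the graft donor site".

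**The concern.** VAS and Oswestry are the patient's own judgements, and they are to be set against the CT verdict on fusion. That comparison is informative only if the judgement is made without knowledge of the verdict. The Protocol lets the scan come first and does not say that the forms must be finished before the result is disclosed. A patient told that the spine has not fused has a reason to report more pain and disability; a patient told that it has fused has a reason to report less. The data could then show a relationship between fusion and clinical success that comes partly or wholly from the disclosure.

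This matters more because the Protocol cites earlier work suggesting that clinical success follows the anterior fusion alone. If patients hear the posterior result before rating themselves, a relationship with posterior status could appear that has nothing to do with the graft bed.

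Knowledge of the product is a second, weaker route. Patients hear the specific risks of the products at consent, and those who then know which one they received may rate with that in mind.

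**Working it through.** The plan gives no figure to reproduce and no rates, effect sizes or error levels bearing on this point. The check is a comparison of the stated timings, a short argument about direction, and counts.

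**1. Order of scan and forms.** Forms: one year (section 3). CT: about one year (section 3), but acceptable at any time beyond nine months (sections 4c and 4d(2)).

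Largest lead of the scan over the forms: 12 − 9 = about 3 months.

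Even if both fall at one year, no order between the result and the forms is stated.

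**2. Effect of knowing the CT result.** Define:
- Δ: the difference in mean rating between unfused and fused patients if nobody knew the result;
- q: the share of patients told their result before scoring, taken as equal in both groups;
- a: the worsening in rating among those told they are not fused;
- b: the improvement among those told they are fused.

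Observed difference = Δ + q(a + b).

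If fusion has no real relation to outcome (Δ = 0), the observed difference is q(a + b), which is wholly produced by disclosure. As written, the Protocol permits any q from 0 to 1 and gives no basis for a or b, so no numerical bias can be quoted. If all forms precede disclosure, q = 0 and the term vanishes whatever a and b are.

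**3. Effect of knowing the product.** Product knowledge distorts the fusion–outcome relationship only if two things hold together: expectations differ by product, and fusion rates differ by product. The second is what the trial sets out to learn. This route is therefore conditional, unlike the one in step 2.

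**4. How far the patient could be kept unaware of the product.** Inputs: five arms of 20 (sections 3 and 4b), one of which requires a harvest from the patient.

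- Total: 5 × 20 = 100 patients.
- No-harvest arms: 4 × 20 = 80 patients.
- All pairwise contrasts: 5 × 4 / 2 = 10.
- Contrasts among the four no-harvest arms: 4 × 3 / 2 = 6.
- Contrasts involving iliac graft: 10 − 6 = 4, which cannot be masked to the patient.

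The absence of a donor site is stated for the three cell-based products. For BMP it is inferred, because BMP is not taken from the patient. Completing the forms before disclosure of the CT result applies to all 100 patients, including the iliac arm.

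**The case against.** **The open design is declared, not contradicted.** Sections 3 and 4b agree, and one arm involves a separate harvest, so full blinding was never available. This stands: the point is a weakness in how the design is fixed, not an inconsistency.

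**The ratings do not touch the main objective.** Posterior fusion is judged on CT, VAS and Oswestry are secondary, and no comparison of them between arms is stated. This also stands and limits the point. It does not remove it, because the bias falls on the one use of the ratings that is stated.

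**Silence on disclosure is not proof of disclosure.** The application form asks for the study protocol and data collection forms to be attached, and these are not shown; they may fix the order. That is possible. But the text at hand sets the scan window and the form date so that the scan may come first, and it sets no safeguard.

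**Masking the product would be imperfect.** It would: the operative report is open to the patient, and the four iliac contrasts stay unmasked. That the other four products cannot be told apart by the patient is an inference from the absence of a donor site; the document does not describe how patients would perceive them.

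**A stronger reading that does not hold.** A reader might infer that the surgeon's knowledge of the arm contaminates the background operation, and so the fusion comparison, and that the allocation should be opened only part-way through surgery. The document does not support this. It gives no operative order and does not say when the surgeon learns the arm. It sets the background surgery as common to all arms: "The decortication part of the fusion is identical for all patients, as is the type of instrumentation (anterior plate and posterior facet screws"), with equal graft volume (about 5 cc) and BMP for every anterior fusion. Departure from that by arm is conjecture. Iliac graft must in any case be harvested before it is placed, so the surgeon must know of it by then.

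**Conclusion.** The concern holds for the secondary outcomes. The Protocol leaves patients unblinded to graft without giving a reason, and it allows the CT to precede the one-year forms by up to about three months with no rule that the forms come before the result. The stated relationship between clinical success and fusion success is therefore open to being created or inflated by disclosure, in up to all 100 patients. Knowledge of the product is a lesser, conditional source of bias that could be reduced in 80 of 100 patients and 6 of 10 pairwise contrasts.

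The conclusion assumes that some patients learn their CT result before scoring and that such knowledge can shift self-ratings. The document neither establishes nor excludes the first, and it gives no basis for sizing the second. Nothing here shows bias in the CT fusion comparison between grafts.

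**What to change.** Add to section 3 (Methods), and mirror in section 4:

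> Every patient completes the VAS and Oswestry forms before being told the CT fusion result. The forms and the CT are scheduled together, so that no result has to be held back.

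This requires the one-year timing of the forms and the wider CT window in sections 4c and 4d(2) to be reconciled, so that both refer to the same occasion.

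Where feasible and covered in the consent, add:

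> Patients in the four arms without iliac harvest are not told which product they received until these forms are complete. This does not apply to the iliac arm, whose four contrasts remain unmasked to the patient. Masking is partial, because patients can access the operative report.

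The cost is Protocol and consent wording and some coordination of visits. The downsides are imperfect masking and, for the second addition, the need for patients to agree beforehand to learn the product name later. The first addition carries most of the benefit and can be adopted alone.

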## 9 Informed Consent

Informed consent is necessary for all research and other activities which involve humans as subjects. It may be secured in several ways, but usually must be documented in some manner. The investigator may determine what method he/she believes would best serve the interest of the subject population. However, the Committee reserves the right, upon review of the research and its attendant risks, to require alternate and/or more stringent means of securing consent. Use of subjects not able to give personal consent for reason of age, mental status, legal or other such status, require that consent be secured from the parents(s) or legal guardian. If it appears necessary to use consent procedures which differ from those normally required, please define and justify their use.

At the top of the Informed Consent form, the study/trial name, the sponsor of the study, and the sponsor-assigned protocol number **MUST** be clearly identified.

In addition, the section on the Informed Consent dealing with problems, questions, etc., must include the following statement:

***"You may also contact [name], Chair, HealthEast Institutional Review Board [contact] or [contact]) with questions regarding your rights as a patient in research studies".***

The Informed Consent must also document the individual who reviewed the informed consent with the subject.

***I confirm that I have personally explained the nature, purpose, duration, and foreseeable benefits and risks of the trial to the participant (or if applicable, the participant's legal representative) named above.***

Person who administered the consent

Signature

Date

Please describe procedures used to obtain informed consent and attach a copy of the informed consent document. These procedures should include an explanation of the following:

- a. In relation to actual data gathering, when will consent be discussed and documentation obtained?

*Consent for this study will be reviewed, discussed, and obtained from the patient preoperatively. The assessment of fusion status occurs post-operatively.*

Will the investigator(s) be securing all informed consent?

Yes       No – If no, please list the name(s) job title(s) and credentials of the individual(s) responsible for obtaining informed consent

- b. What is the reading level of the informed consent? How was this level measured?

10th grade-Flesch-Kincaid readability statistics

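### VAS and ODI are secondary endpoints timed at one year, but no preoperative score is stated and the data-collection list names neither scale

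*Protocol*

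**What the plan says.** The abstract's Methods paragraph (section 3) defines the endpoints and their timing: "Secondary endpoints are patient outcomes for pain and function using standard VAS pain scales and Oswestry Disability Index at one year postoperatively". The same sentence goes on to give the purpose: "Oswestry Disability Index at one year postoperatively will be assessed to ascertain the relationship between clinical success and fusion success". What counts as clinical success is not defined, either as a score level or as a change.

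Neither scale is named anywhere else in the document shown. Section 4, item c, which asks for the data-collection procedures, lists age, the dates of surgery and of the CT scan, "assessment of fusion at follow-up, smoking and osteoporosis status (which may affect fusion status"), and the anterior and posterior graft types. In section 4, item b, the answer about what is asked of subjects covers eligibility and allocation: "Subjects will be asked to agree to be randomized to one of five types of bone graft". It mentions no questionnaire.

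The only preoperative study step described is consent. Section 6, item c says: "Consent will be obtained at the time of preoperative discussion in patients who desire to proceed with fusion surgery". Section 9 agrees: "Consent for this study will be reviewed, discussed, and obtained from the patient preoperatively".

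**The concern.** There are two connected problems.

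- **Internal mismatch.** The abstract names two secondary endpoints that the data-collection answer leaves out. That answer is detailed enough to record the anterior graft, which is the same for every patient.
- **No stated starting value.** The secondary aim compares fused with non-fused patients. Randomisation was to graft and does not balance these two groups. If patients who fail to fuse had worse pain or function before surgery, they would tend to score worse at one year even if fusion had no bearing on symptoms. The protocol lists smoking and osteoporosis because they may affect fusion, but not the preoperative value of the outcome itself.

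This cannot simply be left to an SAP. An SAP can specify an adjustment, but it cannot recover a score that nobody recorded. At stake is the only clinical-outcome aim in the document. The primary objective, posterior fusion by graft type, is untouched, and randomised comparisons between grafts are not biased by the gap.

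**Working it through.** **Text check.** Three statements were checked against the whole document shown, and all three hold: VAS and ODI are given one time point, one year; no preoperative or baseline pain or function score is stated; item 4c names neither scale.

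**No plan figure to reproduce.** The protocol gives no alpha, power, SD or effect size. Its only size figure, 5 groups × 20 = 100, is consistent.

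**Inputs for the illustration**

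- From the protocol: 100 patients in total.
- Assumed: preoperative and one-year scores each have within-group SD 1; correlation r = 0.3 to 0.6; preoperative gap between fused and non-fused patients d = 0.2 to 0.5 SD; no true fusion effect; k = 10, 20 or 30 non-fused patients; two-sided 5% test; 80% power.

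**Step 1: shift in the one-year contrast.** Shift = r × d, which runs from 0.3 × 0.2 = 0.06 SD to 0.6 × 0.5 = 0.30 SD.

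**Step 2: standard error.** SE = √(1/k + 1/(100 − k)). For k = 20, √(1/20 + 1/80) = 0.250. For k = 10 it is 0.333 and for k = 30 it is 0.218.

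**Step 3: false-positive rate without adjustment.** Rate = P(Z > 1.96 − shift/SE) + P(Z < −1.96 − shift/SE). For k = 20:

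- low end: shift/SE = 0.06/0.25 = 0.24, rate 0.057
- high end: shift/SE = 0.30/0.25 = 1.20, rate 0.224

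| Non-fused of 100 | SE | Formula, low to high | Simulated t-test, low and high |
|---|---|---|---|
| 10 | 0.333 | 0.054 to 0.147 | 0.053 and 0.145 |
| 20 | 0.250 | 0.057 to 0.224 | 0.056 and 0.219 |
| 30 | 0.218 | 0.059 to 0.280 | 0.059 and 0.275 |

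The simulation used 20,000 trials per setting. Adjusted for the preoperative score, the false-positive rate was 0.049 to 0.053 throughout.

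**Step 4: precision.** Adjustment multiplies the residual variance by 1 − r², which is 0.91 at r = 0.3 and 0.64 at r = 0.6, a fall of 9% to 36%. The difference detectable with 80% power is 2.802 × SE × √(1 − r²):

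- k = 10: 0.934 SD unadjusted, 0.891 to 0.747 SD adjusted
- k = 20: 0.700 SD unadjusted, 0.668 to 0.560 SD adjusted
- k = 30: 0.611 SD unadjusted, 0.583 to 0.489 SD adjusted

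**The case against.** The strongest reply is that silence in this document proves little. It is an application form that asks for the protocol and any survey or abstraction forms to be attached, and no attachments are shown. The abstract is limited to 500 words. Item 4c introduces its list as what data collection includes, so the list may not be complete. The answer on what subjects are asked to do also omits the CT scan, which is certainly planned. Stating when an outcome is measured does not rule out an earlier measurement. Section 6, item i says "Patients who are followed and treated for their spinal condition and who meet the entry criteria will be enrolled" from the investigator's own practice, so clinic records may already hold scores. All of this stands. It limits the point to what the document states, and does not show that scores will go uncollected.

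The magnitude can also be challenged:

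- The preoperative gap is assumed, and nothing in the protocol says that preoperative symptoms affect fusion. With a gap of zero the error rate is 5%.
- The 22% figure needs both extremes together. At r = 0.5 and d = 0.3 with 20 non-fused, shift/SE = 0.15/0.25 = 0.6 and the rate is about 9%.
- All anterior fusions use BMP, which the abstract describes as giving very high anterior fusion rates, so anterior non-unions may be fewer than 10. With an assumed 5 of 100, the false-positive range is 5.2% to 10%. The detectable difference is 1.29 SD unadjusted and still 1.03 to 1.23 SD adjusted, so for that contrast the scarcity of non-unions limits the analysis more than the missing baseline does.

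These points lower the likely size without removing the defect. If clinical success means a one-year score level, no change score is needed, but the confounding remains. The choice of adjustment model can reasonably sit in an SAP; whether the score is recorded cannot.

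**Conclusion.** The concern holds. As written, the plan would relate fusion status to one-year pain and function in non-randomised groups, without a stated preoperative value, and its data list omits both scales.

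The consequence ranges from trivial to material, depending on two quantities the documents do not give: the correlation between preoperative and one-year scores, and the preoperative gap between fused and non-fused patients. The number of non-fused patients matters too. The damage is confined to one secondary association, so this should be corrected but does not undermine the trial's main question. Confidence is medium, because unseen attachments or clinic records may already supply the scores.

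**What to change.** Add VAS pain and ODI to the item 4c data list at two times: preoperatively and at one year. Take the preoperative scores at the preoperative discussion where consent is already obtained, or abstract them from clinic records if they are held there, and name the source. State whether clinical success means a score level or a change. Relate fusion status to the one-year scores with adjustment for the preoperative score.

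The cost is two short questionnaires per patient before surgery, with no extra visit or scan; if records already hold the scores, it is abstraction only. Two limits remain. Patients already operated on without a recorded score cannot be adjusted. Adjustment also removes confounding by the preoperative score alone, so the result should still be reported as an association.

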## 8 Confidentiality of Data

a. Will any data from this study be a part of permanent record (identifiable to the subject) that will be made available to physician, employer, supervisor, student, FDA, etc.?

NO       YES - Please explain:

*Both the patient and their physician can access their medical record including the operative report which indicates the type of bone graft used in their fusion.*

b. Where, how long, and in what format (paper, electronic, digital) will the data be kept?

*The data will be kept electronically for approximately 10 years.*

c. Describe what security precautions (locked cabinet, password protected, encryption, etc.) that will be taken to protect the data.

*The data will be stored on a password protected computer.*

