## 13 Budget: Attach a budget. If applicable, also include a detailed list of medical related services/procedures and associated costs for this research/project/trial (as outlined on Question 4d).

*The only study-related cost is the follow-up CT scan, which will be paid for by the principal investigator/Midwest Spine & Brain Institute.*

***You have reached the end of this form. Please make sure that you have responded to every question on this application, even if your response is "not applicable".***

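### Posterior fusion on CT is in effect the primary endpoint, yet the design is declared non-blinded and nothing shown withholds graft type from whoever reads the scans

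*Protocol*

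**What the plan says.** Under study design, item 4b of the protocol gives a "Prospective, non-blinded, randomized study design of 5 types of bone graft material applied to 100 patients (20 patients per group"). The Methods paragraph of the Abstract (item 3) is more specific about people: "Neither patient nor surgeon is blinded to the posterior type of bone graft". The CT reader is not mentioned in either place.

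The objective in item 4a is solid posterior fusion. Item 3 says that a limited CT at about one year assesses fusion front and back, and it calls only VAS pain and the Oswestry Disability Index secondary. No endpoint is labelled primary, but posterior fusion on CT fills that place.

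Four other statements bear on who might know the graft when the scan is graded:

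- Item 4c lists "assessment of fusion at follow-up, smoking and osteoporosis status (which may affect fusion status") among the data items, and posterior graft type in the same list.
- Item 4d(3): "Data will be collected by the PI on a personal password protected laptop computer". The only third party named there does the statistical analysis.
- Item 6i: patients "will be enrolled from the PI's clinical practice".
- Item 8a: the patient and "their physician can access their medical record including the operative report which indicates the type of bone graft used in their fusion".

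Item 9a says of the grading only this: "The assessment of fusion status occurs post-operatively".

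**The concern.** Leaving the surgeon and patient unblinded may be unavoidable here. Reading a CT about a year later is a separate act, and it can be masked even when the surgery cannot. The plan labels the whole design non-blinded and does not separate the two.

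Whether a posterior fusion is solid can be a matter of judgement on an uncertain scan. A reader who knows the graft and expects one material to do better could let that expectation settle the call. The protocol itself records prior views: item 3 describes BMP as giving very high fusion rates anteriorly, and item 4b describes the stem cell products favourably. This does not show bias. It shows that expectations exist, which is when masked reading is worth having. Every between-graft comparison for which the reader holds such an expectation is exposed.

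**Working it through.** **1. Reproduce the plan's figure.** 5 groups × 20 patients = 100, as stated in items 3, 4b and 6d. The document gives no alpha, power, expected fusion rate or test, so there is no power calculation to reproduce.

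**2. Is masking stated anywhere?** Each section shown was checked for who reads the CT and what that person knows.

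| Place | On the surgery | On the CT reading |
|---|---|---|
| Item 3, Methods | patient and surgeon not blinded | scan timing and purpose; no reader, no masking |
| Item 4b | whole design non-blinded | no exception made |
| Items 4c, 4d(3) | graft type recorded | fusion recorded in the same data set; the PI collects the data |
| Item 8a | operative report names the graft | patient and physician can open it |
| Item 9a | – | takes place after surgery; no reader, no masking |

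No section shown withholds graft type from the reader. If the reader belongs to the treating practice, the arm is easy to know: the patients are the PI's own, the graft is in the operative report, and the data set holds both items.

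**3. Weight of a single call.** 1/20 = 5 percentage points of an arm's fusion rate.

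**4. Sensitivity of a pairwise comparison.** The counts and the test (two-sided Fisher exact, 20 v 20) are assumptions.

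| Fused, arm A v arm B | p |
|---|---|
| 12 v 18 | 0.0648 |
| 11 v 18 (one call changed in A) | 0.0310 |
| 12 v 19 (one call changed in B) | 0.0197 |
| 12 v 17 | 0.155 |
| 13 v 18 | 0.127 |

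The 12 v 18 case lies close to the threshold by choice. Over all 91 pairs with 8 to 20 fused per arm, a single changed call crosses 0.05 in 17.

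**5. Creating a difference from nothing.** Start from equal counts k/20 in both arms and find the fewest changed calls, in either arm, that give p<0.05: 7 for k = 8 to 12, 6 for k = 13 or 14, and 5 for k = 15 to 18 (for example 15 v 20, p = 0.0471).

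**6. A systematic tilt.** Assume that both arms have the same true fusion rate π and that the reader calls a share u of the non-fused cases in one arm fused. The apparent difference is u(1 − π). For π = 0.5 and u = 0.25 this is 0.25 × 0.5 = 12.5 points. The last two columns give the chance of p ≤ 0.05, from exact binomial sums.

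| π | u | Apparent difference (points) | Fisher | Chi-square |
|---|---|---|---|---|
| 0.5 | 0 | 0 | 2.0% | 4.3% |
| 0.5 | 0.25 | 12.5 | 6.7% | 11.5% |
| 0.5 | 0.50 | 25 | 26.9% | 37.5% |
| 0.8 | 0 | 0 | 2.3% | 5.0% |
| 0.8 | 0.25 | 5 | 3.3% | 6.9% |
| 0.8 | 0.50 | 10 | 7.2% | 13.8% |

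The values of u are illustrative. Nothing in the document says how large u would be, or that it differs from zero.

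**The case against.** The strongest reply is that the point rests on silence. Item 3 lists who is unblinded, and the CT reader is not on the list. The label in item 4b is a one-line answer on a review form and may be shorthand for the same statement. The form asks for a study protocol and data collection forms to be attached. Neither is shown, and some pages were removed, so a masked reading could be described there. None of the facts about the PI's practice, the data collection or the medical record reaches an unnamed reader: a PI can enter a reading made by someone else. The numerical example sits at a boundary, and it takes 5 to 7 altered calls to make a significant result from equal arms. Finally, stored scans could be re-read masked.

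Much of this stands as a limit on what can be claimed. It cannot be said that the reader will know the graft, and the size of any bias is unknown. It does not remove the point. Who reads the main outcome, and with what knowledge, is a matter of design and conduct that belongs in the protocol, so an unseen SAP does not cover it. Item 4b goes beyond silence, because its label covers the whole design. If a masked reading is planned elsewhere, that label still needs correcting. A later masked re-reading is possible, but nothing shown plans one, and masking the first reading is simpler.

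**Conclusion.** The concern holds. As written, the trial can be run with posterior fusion graded by someone who knows the graft. Bias is possible, not shown, and its actual size cannot be derived. What follows from the document is that each changed call is worth 5 points in an arm of 20. On assumed counts, a near-threshold comparison can turn on one call, while a difference made wholly from equal arms needs 5 to 7 altered calls out of 40. The conclusion assumes that the material not shown contains no masked reading. It should be corrected before scans are read. Confidence is medium, because the reader is unnamed and the attachments are unseen.

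**What to change.** In item 4b, replace the non-blinded label with *open-label surgery with masked CT fusion assessment*, and add the same statement after the blinding sentence in item 3. Then state that:

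- whoever already reads the scans does so from de-identified, study-numbered images in random order, without graft type or the operative report;
- the anterior and posterior calls are recorded and locked before graft type is merged;
- someone other than the reader codes the scans and holds the key.

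The cost is protocol wording plus modest effort to code about 100 scans and hold the key. No extra reader, scan, visit or patient is needed. The effort is unbudgeted, since item 13 says "The only study-related cost is the follow-up CT scan". The document names no study staff for it, but the third party already engaged for the statistics could hold the key.

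Two limits remain. Masking reduces bias but does not remove it if the reader recognises a case or the images reveal the graft. It also does nothing for VAS and Oswestry, which are reported by patients who know their graft.
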